## 9.2 SAMPLE SIZE DETERMINATION

The target number of subjects to be enrolled during the study period occurring May 2022 – June 2023 is 100 (50 patients randomized to placebo and 50 to the supplementation group). This target is derived from a similarly conducted study evaluating zinc supplementation (without green tea extract) in a comparable adult population as identified with the current proposal. Based on an assumption that 60% of patients taking study drug and 30% in the placebo group would recover from cold and flu-like symptoms after five days of treatment a total of 84 patients would be sufficient to reach 80% power with a two tailed p value <0.05 to detect differences between groups. The power calculation was

$$N_1 = \left\{ z_{1-\alpha/2} * \sqrt{\bar{p} * \bar{q} * (1 + \frac{1}{k})} + z_{1-\beta} * \sqrt{p_1 * q_1 + (\frac{p_2 * q_2}{k})} \right\}^2 / \Delta^2$$

$$q_1 = 1 - p_1$$

$$q_2 = 1 - p_2$$

$$\bar{p} = \frac{p_1 + kp_2}{1 + K}$$

$$\bar{q} = 1 - \bar{p}$$

$$N_1 = \left\{ 1.96 * \sqrt{0.45 * 0.55 * (1 + \frac{1}{1})} + 0.84 * \sqrt{0.3 * 0.7 + (\frac{0.6 * 0.4}{1})} \right\}^2 / 0.3^2$$

$$N_1 = 42$$

$$N_2 = K * N_1 = 42$$

$p_1, p_2$  = proportion (incidence) of groups #1 and #2  
 $\Delta = |p_2 - p_1|$  = absolute difference between two proportions  
 $n_1$  = sample size for group #1  
 $n_2$  = sample size for group #2  
 $\alpha$  = probability of type I error (usually 0.05)  
 $\beta$  = probability of type II error (usually 0.2)  
 $z$  = critical Z value for a given  $\alpha$  or  $\beta$   
 $K$  = ratio of sample size for group #2 to group #1

performed using an online tool located at <https://clincalc.com/stats/samplesize.aspx> with the following calculations performed:

The anticipated dropout rate is 5% based on a large randomized control study evaluating safety of EGCG following 12 months of treatment using a similar daily dosage as the current proposal. No interim analysis is planned; power calculation is for primary endpoint only.

The primary outcome will be compared using the Chi-square test. Secondary outcomes will be assessed using the Chi-square test for categorical data and student's t-test for continuous data. An exploratory analysis comparing the primary outcome among COVID-19 only patients will also be conducted. All inferential testing will be based on intention-to-treat.

### 9.3 POPULATIONS FOR ANALYSES

All endpoints will be assessed using intention-to-treat analysis. This will include all randomized participants.

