#### 6.1.2 DOSING AND ADMINISTRATION

Eligible patients will be randomized 1:1 to one of the following treatment groups with the following dosing schedule:

1. Zinc/EGCG/ascorbic acid blend: three (3) capsules taken orally two (2) hours following a meal twice daily x5 days.
2. Placebo: three (3) capsules taken orally two (2) hours following a meal twice daily x5 days

The per capsule and total daily dose of each of the individual supplement components is as follows:

267mg green tea extract/capsule (1,600 mg/day)  
33mg elemental zinc/capsule (200 mg/day)  
67mg ascorbic acid/capsule (400 mg/day)

The per capsule and total daily dose of each of the placebo component is as follows:

300mg microcrystalline cellulose/capsule (1,800 mg/day)

Patients will be instructed to begin taking their assigned study product starting the evening of enrollment day and to continue for five consecutive days. For missed doses study participants will be instructed not to double up on doses and to take the prescribed dose at the next scheduled administration time. Study product should be stored away from children so to avoid unintended administration by unauthorized study participants.

Study participants who will be undergoing blood sampling procedures will not be randomized or receive placebo.

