## 7.2 PARTICIPANT DISCONTINUATION/WITHDRAWAL FROM THE STUDY

Participants are free to withdraw from participation in the study at any time upon request.

An investigator may discontinue or withdraw a participant from the study for the following reasons:

- Pregnancy
- Significant study intervention non-compliance
- If any clinical adverse event (AE) necessitating hospitalization
- Disease progression which requires hospitalization
- If the participant meets an exclusion criterion (either newly developed or not previously recognized) that precludes further study participation

The reason for participant discontinuation or withdrawal from the study will be recorded. Subjects who sign the informed consent form and are randomized but do not receive the study intervention may be replaced. Subjects who sign the informed consent form, and are randomized and receive the study intervention, and subsequently withdraw, or are withdrawn or discontinued from the study may also be replaced.

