### 9 STATISTICAL CONSIDERATIONS

#### 9.1 STATISTICAL HYPOTHESES

- Primary Efficacy Endpoint(s):
  1. Combination supplementation with zinc, green tea extract, and ascorbic acid is associated with a decrease in duration and severity of cold and flu-like symptoms following five days of treatment as compared to placebo (superiority analysis). Analysis will be conducted following seven days of follow-up.
- Secondary Efficacy Endpoint(s):

1. Rates of adverse events including, nausea, vomiting, indigestion, worsening of shortness of breath or difficulty breathing, allergic reaction (skin rash, hives, swelling of lips or tongue), and hospitalized or physician visit for study drug related adverse effect will not occur more frequently with combination supplementation with zinc, green tea extract, and ascorbic acid as compared to placebo (superiority analysis). Analysis will be conducted following seven days of follow-up.
2. Rates of patient-reported days missed from work or school and hospitalization or physician office visit(s) for respiratory viral illness related complications will occur less frequently with combination supplementation with zinc, green tea extract, and ascorbic acid as compared to placebo (superiority analysis). Analysis will be conducted following seven days of follow-up.

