#### 9.4.3 ANALYSIS OF THE SECONDARY ENDPOINT(S)

Secondary endpoints are independent of findings from the primary endpoint.

Rates of adverse events will be determined as a percentage of those subjects self-reporting an event compared to the total cohort following seven days of follow-up. Adverse events will be categorically expressed as a single endpoint. Difference in adverse events will be compared using Chi-squared test with incidence rates expressed as percentages. Analysis will be performed based on intention-to-treat. Missing data will be handled by last observation carried forward based on most recent self-reported adverse event (or lack thereof).

Rates of missed days of work or school will be determined as a percentage of those subjects self-reporting a missed day compared to the total cohort following seven days of follow-up. Missed days will be both categorically expressed as a single endpoint with incidence rates expressed as percentages as well as mean days missed with standard deviation. Difference in missed days will be compared using Chi-squared test for categorically expressed missed days (occurrence of any missed day(s) during study follow-up) and student's t-test for mean days missed. Analysis will be performed based on intention-to-treat. Missing data will be handled by last observation carried forward based on most recent self-reported missed day (or lack thereof).

Rates of seeking medical care including physician office visits or hospitalization for worsening respiratory illness will be determined as a percentage of those subjects self-reporting these events compared to the total cohort following seven days of follow-up. A physician office visit or hospitalization for worsening respiratory illness will be categorically expressed as a single endpoint with incidence rates expressed as percentages. Difference in need to seek medical care will be compared using Chi-squared tests. Analysis will be performed based on intention-to-treat. Missing data will be handled by last observation carried forward based on most recent self-reported medical visit (or lack thereof).

---

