#### 9.4.4 SAFETY ANALYSES

Rates of adverse events including, nausea, vomiting, indigestion, worsening of shortness of breath or difficulty breathing, allergic reaction (skin rash, hives, swelling of lips or tongue), and hospitalized or physician visit will be included in secondary analysis as outlined in **Section 9.4.3**. Unsolicited adverse events recorded will be categorized as “other adverse events” and will be described as a incidence rate expressed as a percentage. Each adverse event recorded will be only counted once for any given study subject during the study follow-up period. The 10th revision of the International Statistical Classification of Diseases and Related Health Problems (ICD-10) codes will be used to code adverse events where appropriate. Severity of adverse events will be classified as follows:

- **MILD:** Awareness of signs or symptoms, but easily tolerated and are of minor irritant type causing no loss of time from normal activities. Symptoms do not require therapy or a medical evaluation; signs and symptoms are transient.
- **MODERATE:** Events introduce a low level of inconvenience or concern to the participant and may interfere with daily activities, but are usually improved by simple therapeutic measures; moderate experiences may cause some interference with functioning
- **SEVERE:** Events interrupt the participant's normal daily activities and generally require systemic drug therapy or other treatment; they are usually incapacitating

Expectedness of adverse events will be determined as follows:

- **UNEXPECTED** - nature or severity of the event is not consistent with information about the condition under study or intervention in the protocol, consent form, product brochure, or investigator brochure.
- **EXPECTED** - event is known to be associated with the intervention or condition under study.

Relatedness of adverse events will be determined as follows:

- DEFINITELY RELATED: The adverse event is clearly related to the investigational agent/procedure – i.e. an event that follows a reasonable temporal sequence from administration of the study intervention, follows a known or expected response pattern to the suspected intervention, that is confirmed by improvement on stopping and reappearance of the event on repeated exposure and that could not be reasonably explained by the known characteristics of the subject's clinical state.

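### Adverse events are analysed on all randomized participants, with no safety set for those who took at least one dose; the resulting dilution is probably small and cheap to remove

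*Combined protocol and SAP*

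**What the plan says.** Section 9.3 is two sentences long: "All endpoints will be assessed using intention-to-treat analysis. This will include all randomized participants". Section 9.2 says the same of testing: "All inferential testing will be based on intention-to-treat". Section 9.4.3 applies this to adverse events by name and sets the denominator: "Rates of adverse events will be determined as a percentage of those subjects self-reporting an event compared to the total cohort". It also carries forward the last report, including a report of no event. Section 9.4.4 defines no population of its own; the solicited events "will be included in secondary analysis as outlined in" Section 9.4.3. No safety, as-treated or at-least-one-dose set appears anywhere.

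Three other places bear on who is exposed:

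- Section 7.2: "Subjects who sign the informed consent form and are randomized but do not receive the study intervention may be replaced". Nothing there removes such people from the analysis.
- Section 6.1.2: "Patients will be instructed to begin taking their assigned study product starting the evening of enrollment day". The first dose is therefore taken after randomization and discharge.
- Section 8.1: patients do not leave the emergency department without study drug. Test results may follow by telephone, and a patient who then meets an exclusion criterion is told to stop the product.

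The adverse-event hypothesis in Section 9.1 is that events are not more frequent on active than on placebo. It is labelled a superiority analysis and has no margin.

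**The concern.** For efficacy, analysing everyone as randomized preserves the comparison, and any dilution works against a claim of benefit. For harm, dilution works the other way. A participant who took no capsule cannot have a product-caused event but still counts in the denominator of the assigned arm. The reported rates then do not describe people exposed to the product, and the difference between arms is pulled toward zero, which is also the direction of the Section 9.1 hypothesis. Section 2.3.3 says that an additive risk of nausea is expected, so this is the comparison that most needs clean rates. The plan also does not ask for the number never dosed, so a reader of the results could not judge how much dilution there was.

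**Working it through.** **The plan's own figure.** The only sample-size figure is for recovery (Section 9.2): 60% vs 30%, 80% power, two-sided 0.05. The stated formula gives {1.96·√(0.45·0.55·2) + 0.84·√(0.3·0.7 + 0.6·0.4)}² / 0.3² = 41.9, so 42 per arm and 84 in total, as stated. Section 9.2 says the calculation covers the primary endpoint only, so there is no planned figure for adverse events.

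**Dilution formula.** Let a and p be the event rates among dosed participants on active and placebo, f the never-dosed share in each arm, and u the event rate among the never-dosed, which is the same in both arms because they took nothing.

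- Active, all randomized: (1 − f)a + fu
- Placebo, all randomized: (1 − f)p + fu
- Difference: (1 − f)(a − p), whatever u is

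If the never-dosed report events at the placebo rate (u = p), the risk ratio also shrinks. If they report none (u = 0), the risk ratio stays at a/p, and only the arm rates and the absolute difference shrink.

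**Nausea.** Section 2.3.1 cites 10.2% vs 4.8% from a 12-month EGCG trial. I treat these as rates among dosed participants. The values of f are assumptions; the documents give none.

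| f | Difference, all randomized (points) | Risk ratio if u = p |
|---|---|---|
| 0 | 5.4 | 2.13 |
| 2% | 0.98 × 5.4 = 5.3 | 2.10 |
| 5% | 0.95 × 5.4 = 5.1 | 2.07 |
| 10% | 0.90 × 5.4 = 4.9 | 2.01 |

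The approximate power to detect this excess at 50 per arm is 17.4% with nobody undosed. At f = 5% it is 16.3% for all randomized and 16.7% for the dosed set; at f = 10%, 15.2% and 16.0%. About 373 per arm would be needed for 80%.

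**A larger, illustrative excess.** I take 30% vs 15%, which is not in the documents, and the exact power of the uncorrected two-sided chi-square test. The all-randomized analysis has 50 per arm with active rate 0.30(1 − f) + 0.15f. The dosed set keeps 30% vs 15% but has only 50(1 − f) per arm.

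| f | Power, all randomized | Power, dosed set (n per arm) | Gain (points) |
|---|---|---|---|
| 0 | 44.3% | 44.3% (50) | 0 |
| 5% | 41.1% | 41.6–42.6% (47–48) | 0.5–1.5 |
| 10% | 37.9% | 41.6% (45) | 3.7 |

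The right comparison is along each row, because the dosed set loses the never-dosed participants. Setting the diluted power against the 44.3% of an undiluted 50 per arm would overstate what the change recovers.

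**The case against.** The strongest reply is that this hardly matters here. Product is in hand before discharge (Section 8.1), eligibility requires willingness to follow the regimen (Section 5.1), and the whole anticipated dropout is 5% (Section 9.2). A never-dosed share of 10% is therefore probably high, and at 2% the nausea gap moves by 0.1 point. The comparison has about 17% power for the cited nausea rates with or without a safety set. Low power, and a superiority test with no margin for a hypothesis of no excess, are larger weaknesses. All of this stands and limits the size of the point. It does not make all randomized the right denominator for a rate of harm.

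A second reply is that a dosed set cannot be built perfectly. The missed-dose item exists only for people who answer the calls, and Section 7.3 counts as lost those who miss all seven. That is right, and the fix needs a rule for unknown exposure.

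A reader might also infer more than the documents support:

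- **That the plan expects never-dosed participants in some number.** Section 7.2 only provides for the case.
- **That product will be misdispensed and counted in the wrong arm.** Nothing in the documents suggests that this is likely.
- **That the population was chosen to hide harm.** Section 2.3.3 openly expects additional nausea.
- **That a safety set would restore the power of an undiluted trial of 50 per arm.** The table above shows that it would not.

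**Conclusion.** The point holds as a gap in the definition of analysis populations. The stated rule puts adverse events on all randomized participants, and any never-dosed participants shrink the absolute difference by the factor (1 − f), toward the Section 9.1 hypothesis. The size is probably small: 0.1 to 0.5 of a 5.4-point nausea excess for f of 2–10%, and roughly 1 to 4 points of recoverable power at 30% vs 15% for f of 5–10%. This rests on an assumed f, equal in both arms, and on never-dosed participants having the same event rate in either arm. The power figures further assume that this is the placebo rate. If they report no events, the risk ratio is not biased. The case for the change rests on reporting event rates for people who were exposed, more than on power.

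**What to change.** - In Section 9.3, define a safety set: randomized participants who took at least one dose, grouped by product received.
- Identify dosing from the daily missed-dose item (Sections 6.4 and 8.1), the doses recorded at discontinuation (Section 7.1) and returned product (Section 6.2.1). Take the product received from pharmacy dispensing records, since the missed-dose item does not show it.
- State in advance how unknown exposure is handled. For example, count the participant as dosed if product was dispensed, and add a sensitivity table that excludes such participants.
- Use this set for the adverse-event analyses in Sections 9.4.3 and 9.4.4, and report the never-dosed and unknown-exposure counts per arm.
- Keep all randomized participants for efficacy and as a supportive safety table. Say in Section 7.2 that replaced participants remain in that set.

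The cost is a short paragraph in Section 9.3, cross-references in Section 9.4 and one or two extra tables, with no new data collection. The downside is a slightly smaller set that is no longer strictly as randomized, which the supportive table covers.

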### 9.4 STATISTICAL ANALYSES

#### 9.4.1 GENERAL APPROACH

Descriptive statistics for continues data will be expressed at means with standard deviations and categorical data will be expressed as percentage of total cohort. Inferential testing will use two-tailed p value <0.05 with 95% confidence intervals to determine statistical significance.

#### 9.4.2 ANALYSIS OF THE PRIMARY EFFICACY ENDPOINT(S)

The primary endpoint will be determined from observing the proportion of patients (expressed as percentage) recovered from cold and flu-like symptoms (defined as scoring 0 or 1 daily total symptom severity score) following seven days of follow-up. Recovery from cold and flu-like symptoms will be categorically assessed as a single endpoint. The difference in recovery rates between study drug and placebo will be compared using Chi-squared test and be expressed with 95% confidence intervals. Analysis will be performed based on intention-to-treat. Missing data will be handled by last observation carried forward based on most recent self-reported total daily symptom severity score.

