## 7.3 LOST TO FOLLOW-UP

A participant will be considered lost to follow-up if he or she fails to return for seven consecutive scheduled telephone visits and is unable to be contacted by the study site staff.

The following actions must be taken if a participant fails to return a missed telephone contact for a required study visit:

- The site will attempt to contact the participant to reschedule the missed visit within the same business day as the originally scheduled appointment, counsel the participant on the importance of maintaining the assigned visit schedule, and ascertain if the participant wishes to and/or should continue in the study.
- Before a participant is deemed lost to follow-up, the investigator or designee will make every effort to regain contact with the participant (where possible, 3 telephone call attempts within the same business day). These contact attempts should be documented in the participant's medical record or study file.
- Should the participant continue to be unreachable, he or she will be considered to have withdrawn from the study with a primary reason of lost to follow-up.

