# 8 STUDY ASSESSMENTS AND PROCEDURES

## 8.1 EFFICACY ASSESSMENTS

Patients presenting to MUHC emergency department for cold and flu-like symptoms during the study period will be assessed for eligibility by the admitting physician based on protocol inclusion and

exclusion criteria as previously detailed. Standard evaluation and collection of patient overall health status including past medical history, vital signs, physical exam, necessary imaging, and laboratory assessment will be completed as part of routine care associated with the emergency department visit. Patients enrolled into the study will be randomized and provided study drug the same day of their emergency department visit such that patients will not discharge from the emergency department until they have received their study drug and corresponding instructions for study participation. Testing results including COVID-19 status or positive influenza will be communicated via telephone contact to study patients as part of routine care follow-up and in accordance with MUHC emergency department procedures. Patients meeting exclusion criteria following results of study related testing information will be instructed to discontinue study intervention and follow-up with their primary care provider or other non-study related healthcare provider for appropriate management.

Upon receiving study drug and following discharge from the emergency department study subjects will begin self-administering study product as outlined in section 6.1.2 of this protocol the evening of the day of enrollment. Research staff from the MUHC emergency department will begin contacting patients the following day and daily thereafter for a total of seven consecutive days as described in section 1.3 of this protocol. The following data elements are to be collected each day via telephone visits for the efficacy endpoints:

Primary efficacy endpoints:

Symptom	Severity Score 0 – absent, 1- mild, 2- moderately sever, 3 – very severe
nasal drainage	
nasal congestion	
sneezing	
scratchy throat	
sore throat	
cough	
headache	
hoarseness	
muscle ache	
shivering or feverish	
tiredness	
difficulty in concentration	
Total Severity Score (max: 36 points)	

Recovery from cold and flu-like illness defined as daily total symptom severity score of 0 or 1	Yes or No
day 2	
day 3	
day 4	
day 5	
day 6	

day 7	
day 8	

Secondary efficacy endpoints:

Morbidity Event	Yes or No
missed days from work or school number of days	

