#### 9.4.5 BASELINE DESCRIPTIVE STATISTICS

Baseline characteristics planned to be collected include the following:

- age
- sex
- height
- weight
- ethnicity
- history of asthma
- history of chronic obstructive pulmonary disease (COPD)
- history of diabetes
- COVID-19 status
- history of hospitalization for respiratory condition within the past year

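### LOCF counts dropouts who have not yet recovered as failures in a self-resolving illness, with no sensitivity analysis planned; the loss is small at the planned 5% dropout

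*Combined protocol and SAP*

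**What the plan says.** Recovery is a total symptom score of 0 or 1 after seven days of follow-up, compared between arms by chi-square (section 9.4.2). The missing-data rule is: "Missing data will be handled by last observation carried forward based on most recent self-reported total daily symptom severity score". Section 9.4.9 has the same rule. Section 9.3 sets the population as intention-to-treat: "This will include all randomized participants".

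Scores come only from telephone calls. Under section 8.1, research staff "will begin contacting patients the following day and daily thereafter for a total of seven consecutive days". The list in section 9.4.5 that opens "Baseline characteristics planned to be collected include the following" contains no symptom score.

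Section 9.2 assumes 30% (placebo) and 60% (active) recovered after five days of treatment, and 5% dropout, taken from a 12-month EGCG safety trial. It gives no split of dropout by arm. Section 8.3.5 calls for IRB notice if dropout exceeds 10%.

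Section 7.1 keeps participants who stop for intolerance on their calls. Section 7.3 counts as lost to follow-up someone who "fails to return for seven consecutive scheduled telephone visits" and cannot be reached; only seven calls are scheduled.

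**The concern.** LOCF assumes that the last reported state persists. In an acute viral illness most people improve, so a participant last reached on an early call with a score of 2 or more may well have recovered by Day 8, yet is analysed as a failure. If dropout is equal, both recovery rates fall and the difference shrinks. If dropout is unequal, the arm with more dropout looks worse for a reason unrelated to treatment, and the direction depends on which arm that is. With no alternative analysis planned, a reader of the results could not tell how far they depend on the rule.

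There is also a smaller gap in the wording. A randomized participant with no completed call has no score to carry forward, and no sentence assigns that person an outcome.

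**Working it through.** **The plan's own figure.** Section 9.2 with p1 = 0.30, p2 = 0.60, z = 1.96 and 0.84:

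N1 = {1.96·√(0.45·0.55·2) + 0.84·√(0.30·0.70 + 0.60·0.40)}² / 0.30² = 41.9, so 42 per arm and 84 in total. This reproduces. At the enrolment target of 50 per arm, the same uncorrected formula gives 86.6% power.

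**Effect of LOCF.** Let d be an arm's dropout proportion and F(t) the proportion recovered by call t. LOCF credits a dropout only if already recovered at the last call, so

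observed rate = (1 − d)·F(7) + d·(mean of F over the dropouts' last calls).

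The documents do not give the shape of recovery or the timing of dropout, so three assumed cases are shown:
- A: constant hazard through 30%/60% at day 5, F(t) = 1 − 0.7^(t/5) and 1 − 0.4^(t/5). This gives 39.3%/72.3% at day 7. Dropouts are last reached at calls 1 to 3, where on average 13.1%/29.9% have recovered.
- B: as A, but 30%/60% is the day-7 rate (exponent t/7).
- C, an upper bound on the loss: 30%/60% at the end of follow-up and no dropout yet recovered, so rate = p(1 − d).

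Example, case A at 5%/5%: placebo 0.95 × 0.393 + 0.05 × 0.131 = 0.380; active 0.95 × 0.723 + 0.05 × 0.299 = 0.702; difference 32.2 points.

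Difference in points and power, 50 per arm, two-sided 0.05:

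| Dropout, placebo/active | A | B | C |
|---|---|---|---|
| none | 33.0, 92.5% | 30.0, 86.6% | 30.0, 86.6% |
| 5%/5% | 32.2, 91.0% | 29.1, 84.7% | 28.5, 83.2% |
| 10%/10% | 31.3, 89.3% | 28.3, 82.8% | 27.0, 79.4% |
| 20%/20% | 29.7, 85.6% | 26.6, 78.6% | 24.0, 71.1% |
| 5%/15% | 27.9, 80.8% | 25.4, 73.8% | 22.5, 63.6% |

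In case A at 5%/5%, the loss is 0.5 points if last calls spread over calls 1 to 6, and 1.2 points if every dropout answers only call 1.

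**No true effect, 5% placebo and 15% active.** Bias = −0.10 × (F(7) − mean F at last call). Case A gives −0.10 × (39.3 − 13.1) = −2.6 points on the placebo curve and −0.10 × (72.3 − 29.9) = −4.2 on the active curve. Case B gives −2.0 and −3.7. Case C gives −3.0 (true rate 30%) to −6.0 (60%), with an exact two-sided false-positive rate of 6.4% to 10.1%.

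**Multiple imputation.** A score-based simulation (3,000 trials; assumed starting score mean 14, SD 5) gave differences for full data, LOCF and imputation of 32.9/31.9/32.8 at 5%/5%, 32.9/29.1/32.7 at 20%/20% and 32.7/27.0/32.5 at 5%/15%. These results have not been independently repeated. Dropout depended only on arm and observed scores, and the imputation model used arm and one score without baseline covariates.

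**Why the tipping point must differ by arm.** In case A at 10%/10%, counting all dropouts as failures still leaves 29.7 points. Counting active dropouts as failures and placebo dropouts as recovered leaves 19.7 points (p = 0.048 at expected rates). At 5%/5% the two figures are 31.3 and 26.3 (p = 0.008).

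**The case against.** The strongest reply is that this does not matter at the only dropout rate the plan states. That largely stands: even the upper bound leaves 83.2% power. The serious figures need 10% to 20% dropout or an assumed imbalance. LOCF is pre-specified and simple, and it shrinks the difference when dropout is balanced. The simulation also favours imputation by construction, because its dropout is missing at random. What remains is that LOCF suits this illness poorly, that better information is already collected daily, and that no sensitivity analysis is planned.

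Four stronger readings are tempting, and the documents do not support them.

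- **No-call participants leave the primary result open.** With assumed counts, excluding two active no-calls gives 29/48 v 20/50 (p = 0.043), while counting them as failures gives 29/50 v 20/50 (p = 0.072). But section 9.3 rules out exclusion, and a person with no score has not met the recovery definition, so the text already points to not recovered. With a continuity correction, neither p-value is below 0.05 (0.069 and 0.110).
- **Participants found ineligible after discharge add to the no-calls.** Section 8.1 says only: "Patients meeting exclusion criteria following results of study related testing information will be instructed to discontinue study intervention". Section 7.1 says that stopping the intervention does not end study participation, and withdrawal under section 7.2 is optional. They need not lack calls.
- **Nausea will make dropout unequal.** The cited EGCG trial had more nausea on active (10.2% v 4.8%, section 2.3.1), but section 7.1 keeps intolerant participants on calls.
- **LOCF mishandles participants removed for hospitalization.** It usually counts them as not recovered already. They matter only for how a replacement method is worded.

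**Conclusion.** The concern holds as a minor point at the planned dropout. LOCF understates recovery in both arms. At a balanced 5% it costs about 0.5 to 1.5 points of difference and at most 3.4 points of power (1.5 in case A), and power stays above 80% at 50 per arm. The cost rises with dropout; at a balanced 10% only the upper bound falls below 80% (79.4%). At an assumed 5% placebo/15% active split, the bias with no true effect is about −2 to −4 points under constant hazards with early dropout, and up to −6 points in the upper-bound case. More dropout on placebo would bias the other way.

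These sizes rest on assumed recovery curves and dropout timing. The direction for balanced dropout rests only on the plan's expectation that many participants recover. The missing outcome for no-call participants is a gap in wording that one sentence closes.

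**What to change.** 1. For participants with at least one call, replace LOCF in sections 9.4.2 and 9.4.9 with multiple imputation of end-of-follow-up recovery (at least 20 imputations). Use arm, observed daily scores and a few collected baseline covariates, such as age and COVID-19 status. Pool the risk difference, its 95% CI and its test by Rubin's rules. This replaces the single chi-square test when data are missing. LOCF can stay as a sensitivity analysis.
2. State that randomized participants with no completed call, including anyone replaced under section 7.2, stay in the denominator as not recovered. State that participants removed from calls for hospitalization or worsening illness count as not recovered unless they had already met the recovery definition. Sections 6.3 and 7.1 differ on which events lead to removal and must be reconciled.
3. Add two sensitivity analyses: all missing as not recovered, and a tipping-point analysis whose assumption differs by arm and which also covers no-call participants.

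No new data are needed; the cost is protocol and SAP wording and modest programming. The imputation brings a missing-at-random assumption, which the tipping-point analysis tests. The not-recovered rule costs about 0.7 points in case A for one no-call per arm (33.0 to 32.3). It can itself bias the result if no-calls are unequal: one on placebo and three on active gives 0.723 × 47/50 − 0.393 × 49/50 = 29.4 points.
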